#### 7.2.4 Concomitant Medications and New Antineoplastic Therapy

Concomitant medications will be summarized Enzalutamide, Placebo and Placebo crossover group and by study period on the SAF.

Those medications, including prostate cancer drug therapies, will be coded with World Health Organization Drug Reference List (WHO-DD), and will be summarized by presenting the number and percentage of patients by therapeutic subgroup (ATC 2nd level) and chemical subgroup (ATC 4th level) and preferred WHO name. It will be ordered alphabetically by ATC subgroup and decreasing order of frequency of preferred WHO name within each ATC class. Patients taking the same medication multiple times will be counted once per medication and period.

Concomitant medications are those medications or therapies with at least one dose taken between the date of first dose (inclusive) of enzalutamide and the date of last dose (inclusive) of enzalutamide and up to 30 day safety follow-up visit. All concomitant medications will be summarized.

New antineoplastic prostate cancer therapy will be summarized for patients from the ITT population.

New antineoplastic prostate cancer therapy are therapies with at least one dose taken after the last dose of study drug (enzalutamide or placebo), including cytotoxic and hormone therapies. They are recorded as 'antineoplastic medication' in the eCRF (either prostate cancer concomitant eCRF page, with 'antineoplastic medication' ticked; or on the new prostate cancer drug therapy eCRF page with 'antineoplastic medication' ticked).

All concomitant prostate cancer related medications or therapies reported in the corresponding eCRF will be summarized separately. All (new) antineoplastic prostate cancer therapies (started on or after first dose of study drug date) will also be summarized separately, along with a summary table on the first new antineoplastic prostate cancer after study drug (after placebo or enza [in double blind or OLE]) ended.

All concomitant non prostate cancer related medication which can be classified into several chemical and/or therapeutic subgroups is presented in all chemical and therapeutic subgroups.

All concomitant medications recorded in the eCRF will be listed, as well as all new prostate cancer therapies.

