## 1.4 Risk-Benefit Assessment

Enzalutamide is a novel small molecule designed to have an increased affinity for the AR and more effective suppression of the androgen pathway in the setting of androgen overexpression [Tran et al, 2009]. Enzalutamide has a higher binding affinity to the AR (8 times greater), has no agonist activity and has demonstrated superior AR downstream effects in the setting of androgen overexpression compared to bicalutamide in preclinical studies.

The efficacy of enzalutamide in subjects with metastatic prostate cancer who progressed on ADT has been demonstrated in 5 randomized controlled phase 3 studies including study MDV3100-03 (PREVAIL) in asymptomatic or mildly symptomatic subjects and CRPC2 (AFFIRM) in subjects with more advanced disease who previously received docetaxel. Regardless of study arm, subjects remained on ADT in both PREVAIL and AFFIRM studies. These studies demonstrate a statistically significant advantage of enzalutamide treatment over

- CONFIDENTIAL -

placebo across multiple clinically relevant endpoints such as OS, rPFS, time to first skeletal-related event, time to PSA progression, PSA response rate, best overall soft tissue response, and QoL as measured by the Functional Assessment of Cancer Therapy-Prostate (FACT-P). Study MDV3100-03 (PREVAIL) showed a significant benefit of enzalutamide in time to initiation of cytotoxic chemotherapy.

Study MDV3100-03 (PREVAIL; chemotherapy naïve mCRPC subjects) was stopped after a planned interim analysis (conducted when 540 deaths had been reported) and showed a benefit of the active treatment. The rate of rPFS at 12 months was 65% among subjects treated with enzalutamide, as compared with 14% among subjects receiving placebo (81% risk reduction; HR in the enzalutamide group, 0.19; 95% CI, 0.15 to 0.23; P < 0.001). A total of 626 subjects (72%) in the enzalutamide group, as compared with 532 subjects (63%) in the placebo group, were alive at the data cutoff date (29% reduction in the risk of death; HR, 0.71; 95% CI, 0.60 to 0.84; P < 0.0001). The benefit of enzalutamide was shown with respect to all secondary endpoints, including the time until the initiation of cytotoxic chemotherapy (HR, 0.35), the time until the first skeletal-related event (HR, 0.72), a complete or partial soft tissue response (59% versus 5%), the time until PSA progression (HR, 0.17), and a rate of decline of at least 50% in PSA (78% versus 3%) (P < 0.001 for all comparisons).

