## **3** STUDY OBJECTIVE(S) AND DESIGN

## 3.1 Study Objective(s)

Refer to the study protocol for a full list of study objectives.

Efficacy objective in the open label extension period is to determine the benefit of enzalutamide plus ADT as compared to placebo plus ADT as assessed by overall survival (OS). Additionally, time to new antineoplastic therapy will be summarized descriptively as supportive information in the evaluation of the overall survival endpoint.

Safety objective is to determine the safety of enzalutamide plus ADT as compared to placebo plus ADT.

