#### 6.2 Time to Initiation of a New Antineoplastic Therapy

The initiation of a new antineoplastic therapy is based on the information collected in the (new) prostate cancer therapy CRF pages about all antineoplastic therapies, including cytotoxic and hormone therapies, initiated for prostate cancer subsequent to the study drug.

In patients with a new antineoplastic therapy initiated for prostate cancer, time to initiation of a new antineoplastic therapy (i.e., time to new antineoplastic therapy) is defined as the time interval from randomization to the date of first dose administration of the first antineoplastic therapy.

In patients with no new antineoplastic therapy initiated for prostate cancer, time to start of new antineoplastic therapy will be censored on the last visit date or the date of randomization, whichever occurs last.

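### SAP 7.2.4 classes a therapy as new by any dose after study drug, so continuing background ADT can qualify and the therapy tables may not match the SAP 6.2 events

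*SAP*

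**What the plan says.** SAP 7.2.4 (Concomitant Medications and New Antineoplastic Therapy) gives the main definition of new therapy as "therapies with at least one dose taken after the last dose of study drug (enzalutamide or placebo), including cytotoxic and hormone therapies". It then says where such therapies are found: "They are recorded as 'antineoplastic medication' in the eCRF (either prostate cancer concomitant eCRF page, with 'antineoplastic medication' ticked", or on the page for new prostate cancer drug therapy with the same box ticked.

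The same section adds two further outputs. One has its own timing rule: "All (new) antineoplastic prostate cancer therapies (started on or after first dose of study drug date) will also be summarized separately". The other is "a summary table on the first new antineoplastic prostate cancer after study drug (after placebo or enza [in double blind or OLE]) ended".

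SAP 6.2 defines the events for time to initiation of a new antineoplastic therapy (TTNAnti). It takes all antineoplastic therapies, "including cytotoxic and hormone therapies, initiated for prostate cancer subsequent to the study drug", and dates the event at the first dose of the first such therapy.

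SAP 3.1 states the use of that endpoint: "time to new antineoplastic therapy will be summarized descriptively as supportive information in the evaluation of the overall survival endpoint". SAP 6.3 ends each treatment-emergent window at, among other things, the start of new antineoplastic therapy, without saying which definition applies.

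On the background treatment, Protocol 5.1.3.1 requires ADT by orchiectomy or an LHRH agent in every subject during study treatment. Protocol 3.3 allows it to begin up to 3 months before day 1, or up to 6 months in men given docetaxel.

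**The concern.** A table of subsequent therapy should show what patients were given after study drug that they were not already receiving. A rule based on the date of any dose does not separate the two. Background LHRH therapy is a hormone treatment, it may have begun before day 1, and it may go on after the capsules stop. Nothing in the 7.2.4 timing rule keeps it out.

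Two things are at stake. First, the total of patients with any new therapy, and the first-new-therapy table, could be filled partly with treatment that is not new. That would blur any difference between the arms in later therapy. Second, with three timing rules in use, a patient can be counted in one output and not in another, so the 7.2.4 tables need not reconcile with the TTNAnti events from 6.2. Only the 7.2.4 tables show which agents followed, so a reader who sets them beside TTNAnti will expect them to agree.

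**Working it through.** The plan states no figure on this point, so the check is to apply its rules to example records.

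**The three rules.** Let F be the first and L the last study drug dose.
- Rule A (7.2.4, main definition): some dose of the therapy falls after L.
- Rule B (7.2.4, separate summary): the therapy starts on or after F.
- Rule C (6.2): the therapy starts after L.

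**Example records**, with F = day 1 and L = day 400 (chosen for illustration):

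| Record | A | B | C |
|---|---|---|---|
| ADT started day -60, continues past day 400 | yes | no | no |
| ADT started day 1, continues past day 400 | yes | yes | no |
| LHRH product switched day 200, continues past day 400 | yes | yes | no |
| Other agent started day 395, continues past day 400 | yes | yes | no |
| Antiandrogen days 100 to 120 only | no | yes | no |
| Docetaxel started day 430 | yes | yes | yes |

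Every therapy that meets C also meets A and B, but not the reverse, and A and B do not nest in each other. The first three rows are background ADT that A admits and C rejects. The fourth is foreseeable because Protocol 6.1 makes the start of a new prostate cancer therapy a reason to stop study drug, so a first dose shortly before the last capsule can occur. Read literally, 6.2 does not count it and both 7.2.4 rules do.

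**The recording condition.** Rule A applies only to records with the antineoplastic box ticked. The documents give no instruction on ticking it for background ADT. Among non-orchiectomized men who stop study drug and continue LHRH therapy, the share misclassified therefore runs from 0% (never ticked) to 100% (always ticked).

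**The first-new-therapy table.** The SAP does not say whether first is judged by start date or dose date. If a ticked ADT record is admitted under A and the order is by start date, it precedes any therapy begun after study drug. If the order is by dose date, it comes first whenever the next LHRH dose precedes the other drug.

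**Illustration of size.** All inputs here are assumptions. Let a be the share of subjects flagged through continued ADT, the same in both arms and independent of truly new therapy, and b the share who truly start something new.

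Reported share = 1 - (1 - a)(1 - b), so reported difference = (1 - a) × (b2 - b1).

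With b1 = 0.30 and b2 = 0.50, a true difference of 20 points:

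| a | Reported shares | Difference |
|---|---|---|
| 0 | 30% v 50% | 20 points |
| 0.25 | 47.5% v 62.5% | 15 points |
| 0.50 | 65% v 75% | 10 points |
| 0.80 | 86% v 90% | 4 points |
| 0.95 | 96.5% v 97.5% | 1 point |

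This concerns only a total of patients with any new therapy. The documents do not locate a anywhere between 0 and 1.

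**The case against.** The strongest reply is the tick box. If sites do not tick it for background ADT, rule A never sees those records and the tables are unaffected. That stands, and it is why the point is about what can be counted, not what will be. It does not cure the rule: the tick is not a timing condition, hormone therapies are expressly included, the concomitant page is an accepted source, and no convention for ADT is given.

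Second, 7.2.4 summarizes medications by ATC class and preferred name. If that layout is used for new therapies, LHRH agents sit on their own rows and docetaxel stays visible. This also stands, and it confines the distortion to an any-therapy total and the first-new-therapy table.

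Third, this SAP supplements the main SAP (version 3.0) and refers to table specifications, neither of which is at hand. ADT handling may be settled there. That is possible, but 7.2.4 states its own rule and does not defer to them.

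A reader might also infer more than the documents support:
- **That the 7.2.4 table is the output meant to support OS.** SAP 3.1 gives that role to TTNAnti, which continuing ADT does not enter under 6.2.
- **That the protocol documents ADT continuing after study drug stops.** Protocol 1.4 says only "Regardless of study arm, subjects remained on ADT in both PREVAIL and AFFIRM studies", which is silent on that period. Protocol 5.1.3.1 covers study treatment only. Continuation is plausible but is an assumption.
- **That the dose-after rule shortens the treatment-emergent window.** SAP 6.3 refers to the start of a therapy and does not cite 7.2.4. All that can be said is that 6.3 names no definition.

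**Conclusion.** The point holds as a defect of definition in descriptive outputs. SAP 7.2.4 uses a dose-after rule that can label continuing background LHRH therapy as new, and that rule conflicts with a second rule in the same section and with 6.2. The subsequent-therapy and first-new-therapy tables may therefore not match the TTNAnti events.

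The size cannot be computed from the documents and may be zero. Any effect of continuing ADT rests on two assumptions: that some men continue LHRH therapy after their last capsule, and that some of those records are ticked as antineoplastic. The inconsistency between the three rules needs neither assumption.

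It would be wrong to conclude that the OS comparison is compromised. The OS test does not use this classification, and the 6.2 endpoint is not affected by continuing ADT. The tables are descriptive, but a start-date rule is clearly better and costs little.

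**What to change.** In SAP 7.2.4, replace the dose-after rule with a start-date rule aligned with 6.2: a course of antineoplastic therapy for prostate cancer that starts after the last study drug dose. Count the restart of an agent used before entry, so that docetaxel given again to men who had it earlier is not lost. Exclude continued background ADT, a switch of LHRH product, and antiandrogen given only to prevent flare (allowed by Protocol 5.1.3.4).

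Use the same flag for the first-new-therapy table, and cite it in 6.3 for the start of new antineoplastic therapy.

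Keep the TTNAnti derivation as it stands. SAP 7.4.1 records that this endpoint was already tested at the primary rPFS analysis, and a redefinition would make the update non-comparable. Report separately any therapy started before the last study drug dose, so that overlapping starts are visible without changing the endpoint.

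The cost is SAP wording, one derived flag and a limited medical review of ADT and flare entries. SAP Section 1 allows revision before hard lock; if that has passed, the change can be justified in the clinical study report.

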#### 7.3 Study Drugs

#### 7.3.1 Exposure

The following information on drug exposure will be presented for Enzalutamide, Placebo and Placebo crossover group on the SAF.

- The duration of exposure (number of months) to study medication will be summarized using descriptive statistics, including 10%, 25%, 75% and 90% percentiles.
- Number and percentage of patients on study drug at 6 months and at year 1, 2, 3, and 4 (that is with duration of exposure superior or equal to day 182, 365, 730, 1095, and 1461).
- Number and percent of patient with dose reductions or interruptions, the reasons for these, as well as the number of these per patient
- Descriptive statistics for the average daily dose of the drug patient was exposed to
- Time to study drug discontinuation will be analyzed using the same analysis methods as OS, but formal statistical test will not be conducted.

#### 7.3.2 Compliance

Compliance data will be presented for the SAF, on subjects whose total study drug count and first and last days of treatment are known.

Overall compliance will be summarized in two ways for the SAF:

- Descriptive statistics will be presented by treatment group.
- Percent compliance will be categorized according to the following categories for each age group and overall by treatment group:
  - $\circ$  less than 70%
  - o at least 70%, less than 90%
  - $\circ$  at least 90%, less than 110%
  - o greater than 110%
  - o Unknown.

Treatment compliance details, including all data relevant to the calculation, will be listed for each subject by study visit and overall for all randomized subjects.

#### 7.4 Analysis of Efficacy

Efficacy analyses will be conducted on the ITT population unless otherwise specified.

The categories '1-5 cycles' and '6 cycles' used at randomization for the stratification factor 'prior docetaxel use' are regrouped in the stratified analyses because of the small number of randomized patients with 1 to 5 cycles of docetaxel as prior medication. This stratification factor therefore becomes prior docetaxel use (yes versus no) in the stratified analyses.

The statistical analyses in this SAP follow the methods already outlined in the main study SAP and include additional sensitivity and subgroup analyses.

#### 7.4.1 Overall Survival

At the time of the primary analysis of rPFS, the interim analysis of OS was not significant (84 deaths from any cause, 39 in Enzalutamide + ADT group and 45 in Placebo + ADT group, p=0.3361 from stratified log-rank test). The final analysis of OS will be conducted when approximately 342 events (death from any cause) have occurred.

At the time of the primary analysis of rPFS, the following six key secondary endpoints were tested: OS, Time to PSA progression, time to initiation of a new antineoplastic therapy, the rate of PSA decline to <0.2ng/mL (PSADecR), objective response rate and the time to deterioration in urinary symptoms from the QLQ-PR25. To maintain the family-wise 2-sided type I error rate at 0.05, a parallel testing strategy between OS (with allocated type I error rate 0.04) and the other five endpoints (with allocated type I error rate 0.01) was performed, as summarized in Figure 1.

#### Figure 1 Testing Strategy for the Primary and Six Selected Secondary Endpoints

rPFS: radiographic progression-free survival; OS: overall survival; TTPP: time to PSA progression; TTNAnti: time to initiation of a new antineoplastic therapy; PSADecR: rate of PSA decline to <0.2 ng/mL; ORR: objective response rate; TTUri: the time to deterioration in urinary symptoms from the QLQ-PR25 \*OS will be tested at 0.05 only, if all other 5 secondary endpoints analyses are statistically significant at 0.01.

As the analysis for time to deterioration in urinary symptoms from the QLQ-PR25 was not significant, the final analysis of OS will be conducted at the level of significance of 0.04 (2-sided). The effect of Enzalutamide+ADT compared to placebo+ADT will be tested using a log-rank test stratified by prior docetaxel use (yes versus no) and disease volume (low versus high).

The null and alternative hypotheses to be tested are as follows:

The null hypothesis: OS for Placebo+ADT and Enzalutamide+ADT are not different The alternative hypothesis: OS for Placebo+ADT and Enzalutamide+ADT are different

The following SAS code will be used to compute the Kaplan-Meier estimates and curves, and the stratified log-rank test:

PROC LIFETEST DATA=INPUT ATRISK

```
PLOTS=SURVIVAL(CB)
OUTSURV=SURVPL
ALPHA=0.04
ALPHAQT=0.04 METHOD=KM;
TIME AVAL*CNSR(1);
STRATA STRATUM/ GROUP=TREATMENT;
RUN;
where INPUT is the input dataset
```

AVAL is the time to the event variable,

CNSR is 0 (patients with events) or 1 (patients without no event, i.e. patient censored) STRATUM is the stratification variable (volume of disease and prior docetaxel use) TREATMENT is the treatment variable

Kaplan-Meier methods will be used to estimate the distribution of OS events by treatment group. The median OS will be estimated using the corresponding 50th percentile of Kaplan-Meier estimates. A two-sided 95% confidence interval will be provided for this estimate by use of the Brookmeyer and Crowley method. The 25th percentile and the 75th percentile of OS will also be provided. A Kaplan-Meier plot by treatment group will be presented. The estimates of the event free rate on a 3-monthly basis up to 1 year and every 6 months thereafter will be summarized by treatment group, as long as at least 10 patients are at risk.

The benefit of Enzalutamide+ADT compared to placebo+ADT will be summarized by a single HR with its 95% CI based on a Cox regression model stratified for the prior docetaxel use and disease volume. The null and alternative hypotheses regarding OS can be rephrased in terms of the HR,  $\lambda_{ArmA} / \lambda_{ArmB}$ , where  $\lambda_{ArmA}$  represents the hazard of OS for Enzalutamide+ADT and  $\lambda_{ArmB}$  represents the hazard of OS for placebo+ADT. A HR of < 1 indicates that the OS is prolonged for patients randomized to Enzalutamide+ADT compared with patients randomized to placebo+ADT. The null and alternative hypotheses, respectively, can be written as follows:

$$H_0: \frac{\lambda_{ArmA}}{\lambda_{ArmB}} = 1 \qquad H_1: \frac{\lambda_{ArmA}}{\lambda_{ArmB}} \neq 1$$

The estimated HR of Enzalutamide+ADT to placebo+ADT,  $\lambda_{ArmA} / \lambda_{ArmB}$ , and its 95% confidence interval will be provided.

SAS PROC PHREG will be used for the analysis with the "DISCRETE" option for tie breaker as follows:

```
PROC PHREG DATA=ADTTE;
WHERE PARAMCD=&ENDPOINT;
CLASS TRTP(REF='PLACEBO + ADT') STRATUM1 STRATUM2;
MODEL AVAL*CNSR(1)= TREATMENT / RL TIES=DISCRETE;
STRATA STRATUM1 STRATUM2;
RUN;
```

```
where INPUT is the input dataset
```

AVAL is the time to the event variable,

CNRS is 1 (patients with no events) or 0 ( patients with events) STRATUM are the stratification variables (volume of disease and prior docetaxel use) TREATMENT is the treatment variable

If the estimate of the HR  $\lambda_{ArmA} / \lambda_{ArmB} < 1$  and the results from the log-rank test lead to the rejection of H0 in favor of HA, then it will be concluded that Enzalutamide+ADT prolongs OS compared to placebo+ADT.

The primary cause of death will be summarized and listed.

The median follow-up time on study will be calculated as the 50th percentile of Kaplan-Meier estimates from the OS time analysis when reverting the censoring (flag).

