# 7.4 Analysis of Efficacy

## 7.4.1 Analysis of Primary Endpoint

rPFS is defined as the time from randomization to the first objective evidence of radiographic disease progression as assessed by central review or death (defined as death from any cause within 24 weeks from study drug discontinuation), whichever occurs first.

Radiographic disease progression is defined as progressive disease by RECIST version 1.1 for soft tissue disease or by appearance of 2 or more new lesions on bone scan.

The effect of enzalutamide plus ADT compared to ADT will be tested using a stratified log-rank test at the level of significance of 0.05 (2-sided). The benefit of enzalutamide plus ADT compared to ADT will be summarized by a single HR with its 95% CI based on the Cox regression model. Kaplan-Meier curves will be used to estimate the distribution of the duration of rPFS. Median duration of rPFS will be estimated using the corresponding 50% percentile of the Kaplan-Meier estimates. A 2-sided 95% CI will be provided for these estimates.

The analysis will be conducted when at least 262 rPFS events have occurred.

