## OS:

The duration of OS is defined as the time from randomization to death from any cause. OS will be analyzed as for rPFS.

The O'Brien-Fleming alpha spending function will be used to determine the stopping boundaries based on the number of events observed at the interim look to control the overall 2-sided alpha at 0.05 or at 0.04 (as described in Figure 2).

EudraCT number 2015-003869-28

- CONFIDENTIAL -

The interim analysis of OS expected at the time of the final analysis of rPFS will be performed at an expected significance level of 0.006 based on approximately 170 death events. If this interim analysis of OS is not statistically significant, the final analysis of OS is planned when approximately 342 deaths are observed to ensure an adequate number of events for the evaluation of OS.

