#### 7.4.2 Time to Initiation of a New Antineoplastic Therapy

This will be analyzed using the same analysis methods as OS, but formal statistical test will not be conducted.

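### The SAP text and protocol give a 95% interval for median OS, but the printed PROC LIFETEST code sets ALPHA and ALPHAQT to 0.04, which gives 96% limits

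*SAP*

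**What the plan says.** SAP section 7.4.1 introduces the code with "The following SAS code will be used to compute the Kaplan-Meier estimates and curves, and the stratified log-rank test". The options in that step include ALPHA=0.04 and "ALPHAQT=0.04 METHOD=KM". After the code, the text turns to the median by treatment group and states: "A two-sided 95% confidence interval will be provided for this estimate by use of the Brookmeyer and Crowley method". It gives no confidence level for the 25th and 75th percentiles, the event-free rates or the plotted bands.

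The protocol reaches the same 95% by cross-reference. In section 7.4.2 the OS paragraph says "OS will be analyzed as for rPFS", and section 7.4.1, on the Kaplan-Meier median of rPFS, says "A 2-sided 95% CI will be provided for these estimates".

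Two further SAP endpoints take over the OS methods without a test. Section 7.3.1 says "Time to study drug discontinuation will be analyzed using the same analysis methods as OS, but formal statistical test will not be conducted", and section 7.4.2, on new antineoplastic therapy, says "This will be analyzed using the same analysis methods as OS, but formal statistical test will not be conducted".

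The value 0.04 appears elsewhere only as a test level. It is the share of type I error allocated to OS in the parallel testing strategy, the level used for the 342-death sample size, and the level of the final OS log-rank test. The OS hazard ratio interval in SAP 7.4.1 is specified at 95%.

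**The concern.** The text and the code cannot both be followed. ALPHAQT sets the level of the limits for the survival-time quartiles, including the median, and ALPHA sets it for the survival function and its bands. Neither option changes the log-rank p-value, which is compared with 0.04 directly. The two settings therefore do nothing for the test and alter only the intervals.

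Median OS with its interval will be a headline result. As printed, the code would produce 96% limits for a quantity that the text and the protocol describe as 95%, and a programmer or validator would have to guess which instruction governs. If the same step is reused for time to study drug discontinuation and time to new antineoplastic therapy, the 0.04 goes with it, although neither endpoint has a test that could explain that value.

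**Working it through.** **1. Is 0.04 correct as the test level?** The inputs are in SAP section 4: target HR 0.73, 80% power, 4% significance level, 342 deaths. Allocation is 1:1 (SAP section 3.2).

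- Schoenfeld: 4(z₀.₉₈ + z₀.₈₀)² / (ln 0.73)² = 4(2.0537 + 0.8416)² / (0.3147)² = 338.6, so 339 deaths.
- Freedman: [(1 + 0.73)/(1 − 0.73)]² × (2.0537 + 0.8416)² = 344.2, so 345 deaths.

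The planned 342 lies between these, and 342 deaths give 80.4% power by the Schoenfeld formula. So 0.04 is right for the test. The conflict is confined to the intervals.

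**2. Levels side by side.**

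| Place | Quantity | Level |
|---|---|---|
| SAP 7.4.1, text | median OS | 95% |
| SAP 7.4.1, code, ALPHAQT=0.04 | quartiles including median | 1 − 0.04 = 96% |
| SAP 7.4.1, code, ALPHA=0.04 | survival curve and bands | 1 − 0.04 = 96% |
| SAP 7.4.1, text | quartiles, event-free rates, bands | not stated |
| SAP 7.4.1, text | OS hazard ratio | 95% |
| Protocol 7.4.2 through 7.4.1 | Kaplan-Meier median | 95% |

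No place in either document asks for 96%.

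**3. Size in normal-theory terms.** z₀.₉₈ / z₀.₉₇₅ = 2.0537 / 1.9600 = 1.048, so a 96% interval is about 4.8% wider.

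**4. Size in months.** The SAP's OS assumptions were simulated: exponential medians of 40 and 55 months, 550 patients per arm, analysis at death 342, Brookmeyer-Crowley limits on the log-log scale, no dropout, 1000 trials per setting. The documents do not give the accrual length, so uniform accrual over 24, 36 and 48 months was assumed. Results for the placebo arm:

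| Assumed accrual | Mean drop in lower limit, 95% to 96% | 95% lower limit estimable | 95% upper limit estimable |
|---|---|---|---|
| 24 months | 0.16 months | 85% of trials | 0% |
| 36 months | 0.27 months | 99.5% | 2.7% |
| 48 months | 0.29 months | 100% | 42% |

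Repeat runs moved the drops by a few hundredths of a month. In the enzalutamide arm the 95% lower limit was estimable in about 18%, 46% and 83% of trials at 24, 36 and 48 months. At 48 months it dropped by 0.24 to 0.29 months.

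**The case against.** Nothing inferential depends on this. The OS conclusion rests on the log-rank test at 0.04 and on an estimated HR below 1. That is true, and the point is rated accordingly.

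The printed step may not be the one that yields the promised interval. The text wants medians by treatment group, while the step stratifies by the randomisation factors with treatment as the GROUP variable, which serves the stratified test. The code also reads like a template, since dataset and variable names differ between the listing and its legend. Table formats are left to separate specifications, so a mislabelled output is a possibility and not an established fact. This stands as a caution. It does not remove the conflict, because the SAP says this code will compute the Kaplan-Meier estimates, and if another call produces the medians its level is not shown.

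The protocol's 95% is indirect. The sentence was written for rPFS, and the general time-to-event paragraph in protocol 7.4.2 attaches 95% only to the HR. That is correct, but the SAP's own sentence is explicit for OS.

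The month figures are weakly anchored. The 4.8% presumes two finite limits, yet the upper limit is seldom estimable. The model expects 84 deaths, the number reported at the interim OS analysis, at 16.3, 20.2 and 23.5 months, before accrual ends in each scenario. It expects 342 deaths by roughly 37 to 51 months, whereas the SAP of July 2021, more than five years after the planned 1Q2016 start, still places them in the future. Accrual of 48 months also sits badly with the December 2019 US approval that the protocol mentions. The months should be read as an order of magnitude only.

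A deliberate 96% interval, chosen to match the test, is conceivable. The 95% sentence would then be wrong, and the 95% HR interval would not fit that intent, so the passages would still need reconciling.

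**Conclusion.** The inconsistency is real, and nothing in either document resolves it. As printed, the code does not deliver the 95% interval for median OS that the SAP text states and the protocol implies. The effect is small: about 4.8% in nominal width, or a few tenths of a month in the lower limit under the SAP's exponential model with an assumed accrual length. It concerns reporting only. Type I error, power, the 342-death target and the OS decision rule do not change. The conclusion rests on the usual meaning of the two options in PROC LIFETEST and on the SAP's statement that this code will be used. That the 0.04 was carried over from the test level is an inference from the matching value.

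**What to change.** Set ALPHA=0.05 and ALPHAQT=0.05 in the printed step, and in any other call that produces the medians by arm. Add one sentence giving the level for the quartiles, event-free rates and plotted bands. Use the same setting where the OS methods are applied to the untested endpoints in SAP 7.3.1 and 7.4.2. If 96% was intended, the text should say so, give the reason and note the departure from the protocol.

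The cost is two code options and one sentence. The log-rank test at 0.04 stays as it is.

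Optional, and purely presentational: label the 95% HR interval as descriptive, or show a 96% interval beside it. With SE(log HR) ≈ 2/√342, the 4% test needs an estimated HR below exp(−2 × 2.0537/√342) = 0.801, while the 95% interval excludes 1 below exp(−2 × 1.9600/√342) = 0.809. An estimate between the two would give a 95% interval that excludes 1 alongside a test that fails.
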